16.2.2.3. MI method – range data

The sensitivity analysis for key secondary endpoints (SGRQ total score and weekly mean E-RS total score), the main analysis of TDI and EQ-5D-5L will be performed using MI based on the missing data assumption MAR as described in the section 16.2.2.1 of the SAP. Additionally, in the first 2 steps the MIN= and MAX= options will be used to restrict the possible values that can be drawn referred to each endpoint (Laura Rodwell, 2014).

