3.2.3 Other Endpoints

- Moderate/severe COPD exacerbation frequency over 24 Weeks (this individual study and pooled with data from study RPL554-CO-301).
- Time to first moderate/severe COPD exacerbation over 24 Weeks (this individual study and pooled with data from study RPL554-CO-301).
- Study withdrawal before 24 Weeks.
- EuroQol-5-Domain Questionnaire (EQ-5D-5L) at Week 12 (change from baseline).
- Healthcare Resource Utilization (HRU) over 24 Weeks.
- Average FEV₁ AUC_{6-12h} post-dose at Week 12 (change from baseline).
- Ensifentrine concentrations (sparse sample collection) at Weeks 6, 12, and 24.
- Patient genotype/phenotype including but not limited to cytochrome P-450 (CYP)2C9 and CYP2D6 metabolic activity.
- Interleukin (IL)-6, IL-8, and C-reactive protein at Weeks 12 and 24.

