16.3.1.2. EQ-5D-5L

Quality of Life (QoL) was assessed using the EQ-5D-5L questionnaire. This questionnaire

consists of 5 domains: mobility, self-care, usual activities, pain/discomfort and anxiety/depression with 5 possible responses from 1 (no problem) to 5 (unable). The sixth item, referred to as a visual analogue scale (VAS) score, is an index score to self-rate health from 0 (worst) to 100 (best). Each of the 5 domains will be summed through weighing system into a health index. The health index and VAS score will be analysed and listed and 5 domains will be only listed. It is not possible to have missing items in the questionnaire, as the data are collected in an electronic tablet which doesn't allow patients to skip between items. The weighting system is described in APPENDIX 6 of the SAP.

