16.3.2. MISSING DATA METHODS FOR OTHER EFFICACY VARIABLES

For EQ-5D-5L missing data will be imputed using imputation described in section 16.2.2.3 of the SAP and FEV₁ AUC_{6-12h} missing data will be imputed using imputation described in section 16.2.2.1 of the SAP. Morning trough FEV₁ responder missing data will be handled as described in sections 16.2.2.2 of the SAP. E-RS total score responder missing data will be imputed similar to the SGRQ total score responder analysis as described in sections 16.2.2.3 of the SAP.

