16.3.3. ANALYSIS OF OTHER EFFICACY VARIABLES

Change from baseline to average FEV₁ AUC_{6-12h} will be analyzed using ANCOVA approach and missing data will be imputed using imputation, as described in sections 16.1.3 and 16.2.2.1 of the SAP, respectively.

[figure not shown]
Model assumptions will be tested and solved, if failed, as per section 16.1.3 of the SAP.

The number of moderate or severe COPD exacerbations will be analyzed using a negative binomial model adjusting for treatment, region, actual background medication strata and actual smoking strata, as well as using log study time (years) as an offset. For study time, Visit 5 will be taken into account for completer patients, and End of Study visit or last contact date for withdrawal patients. The treatment difference from the negative binomial model will be expressed as an annualized risk ratio. The data will also be summarized by treatment group over duration of the study period.

Time to first moderate or severe COPD exacerbation during the study period will be presented as per following:

- Primary approach: Analyzed using the log-rank test, stratified by region, actual background medication strata and actual smoking strata. Summary of number of patients with events and number of patients censored will be summarized. Outcome visualized using a Kaplan-Meier plot.
- Sensitivity analysis: Analyzed using Cox proportional hazards Regression model stratified by region, background medication strata and smoking strata. Patients without exacerbations will be censored at last day in the treatment period, including period of recording after possible treatment withdrawal. The treatment difference in the Cox model will be expressed as a hazard ratio.

Testing proportional hazard assumptions:

1. Check that the covariates are independent of each other through proc phreg in SAS software.
2. Check that the hazard (hazard ratio) is independent of time through $\log(-\log(\text{survival}))$ vs $\log(\text{time})$ plot and an interaction test for treatment times $\log(\text{time})$.

The health index and VAS score for EQ-5D-5L questionnaire will be analyzed using ANCOVA approach, as described in section 16.1.3 of the SAP, with data imputation described in section 16.2.2.3 of the SAP.

HRU over 24 weeks will be summarized for each event and for overall count.

Analysis for the genetics data is described in section 18 of the SAP.

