APPENDIX 6. EQ-5D-5L WEIGHTS

To account for this study collecting data in multiple countries, different EQ-5D-5L weights will be used depending on the country, as presented in Table 5.

Table 5: EQ-5D-5L geographical region categorisation

Countries	Version used
Eastern Europe: Bulgaria, Hungary, Poland, Slovakia, Estonia	Poland (EQ-VT v2.0)
Western Europe: Belgium, Denmark, Spain	England (EQ-VT v1.0)
North America: US, Canada	US (EQ-VT v2.0)

Data collected from questionnaire will be numbered, as presented in Table 6.

Table 6: EQ-5D-5L data collection

Variable name	Mobility	Self-care	Usual Activities	Pain/Discomfort	Anxiety/Depression	Health score	VAS
Variable score range	1-5	1-5	1-5	1-5	1-5	5-digit code for EQ-5D-5L	0-100
Data row example	2	3	1	1	1	23111	83

The health score is a combination of the scores for the 5 questions (mobility, self-care, usual activities, pain/discomfort and anxiety/depression) in the order they are collected, as shown in the data row example in Table 6.

POLAND

The health index is calculated by first summing all weights related to the scores from the questionnaire and subtracting it from 1, i.e. for data row example in Table 6 the health index would be 0.928. Weights related to each score are presented in Table 7.

Table 7: Weights

Variable	Score	Weights
Mobility	1	0
	2	0.025
	3	0.034
	4	0.126
	5	0.314
Self-care	1	0
	2	0.031
	3	0.047
	4	0.111
	5	0.264
Usual Activities	1	0
	2	0.023
	3	0.040
	4	0.097
	5	0.205
Pain/discomfort	1	0
	2	0.030
	3	0.050
	4	0.261
	5	0.575

[figure not shown]
Anxiety/ depression	1	0
	2	0.018
	3	0.029
	4	0.108
	5	0.232

ENGLAND

The health index is calculated by first summing all weights related to the scores from the questionnaire and subtracting it from 1, i.e. for data row example in Table 6 the health index would be 0.879. Weights related to each score are presented in Table 8.

Table 8: Weights

Variable	Score	Weights
Mobility	1	0
	2	0.058
	3	0.076
	4	0.207
	5	0.274
Self-care	1	0
	2	0.050
	3	0.080
	4	0.164
	5	0.203
Usual Activities	1	0
	2	0.050

	3	0.063
	4	0.162
	5	0.184
Pain/discomfort	1	0
	2	0.063
	3	0.084
	4	0.276
	5	0.335
Anxiety/ depression	1	0
	2	0.078
	3	0.104
	4	0.285
	5	0.289

US

The health index is calculated by first summing all weights related to the scores from the questionnaire and subtracting it from 1, i.e. for data row example in Table 6 the health index would be 0.797. Weights related to each score are presented in Table 9.

Table 9: Weights

Variable	Score	Weights

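### The main EQ-5D-5L analysis uses range-limited imputation, which lowers imputed health-index values and biases the treatment difference in a direction set by each arm's missing rate

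*SAP*

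**What the plan says.** SAP 16.2.2.3 states that "the main analysis of TDI and EQ-5D-5L will be performed using MI based on the missing data assumption MAR", and adds that "in the first 2 steps the MIN= and MAX= options will be used to restrict the possible values that can be drawn". The same sentence gives this method only sensitivity status for SGRQ total score and weekly mean E-RS.

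SAP 16.3.2 repeats the assignment: "For EQ-5D-5L missing data will be imputed using imputation described in section 16.2.2.3". SAP 16.3.3 names the two outcomes and the model: "The health index and VAS score for EQ-5D-5L questionnaire will be analyzed using ANCOVA approach", again with the 16.2.2.3 imputation.

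SAP Appendix 6 defines the index: "The health index is calculated by first summing all weights related to the scores from the questionnaire and subtracting it from 1". Three value sets are used, because "different EQ-5D-5L weights will be used depending on the country". The numerical limits for MIN= and MAX= are not written out.

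The only EQ-5D-5L sensitivity analysis, in SAP 16.3.4, uses on-treatment data without imputation. EQ-5D-5L at Week 12 is listed among the other endpoints (Protocol 3.2.3) and is not in the hierarchy of SAP 7.4.

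**The concern.** The ANCOVA estimates a difference in means, so what matters is that imputed values have the right mean. An imputed value need not be an attainable score. Cutting off the upper part of the draws moves the mean down, and more so for a patient predicted close to 1. The index is therefore understated among imputed patients in both arms.

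The treatment difference inherits the gap between the two arms' losses. Each arm's loss grows with its missing rate and with its closeness to the ceiling, so the bias can run either way. If placebo patients drop out more often, it can favour ensifentrine. SAP 3.3 drops the SGRQ non-responder analysis out of exactly that worry, so the same care is reasonable here. No planned output would show the effect of the limits, because no unrestricted imputation of EQ-5D-5L is planned.

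**Working it through.** **The plan's own figures.** The SAP gives no mean, SD, effect or missing rate for EQ-5D-5L, so there is no power or bias figure to reproduce. Its worked index values for state 23111 can be checked:
- Poland: 1 − 0.025 − 0.047 = 0.928, as stated.
- US: 1 − 0.096 − 0.107 = 0.797, as stated.
- England: 1 − 0.058 − 0.080 = 0.862, where the SAP prints 0.879. This is a separate slip with no bearing on this point.

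In all three sets, state 11111 scores 1 − 0 = 1, so the ceiling is 1.

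**Which step matters.** EQ-5D-5L is collected at Day 1 and Week 12 only (Protocol 1.3). With baseline present the missing pattern is already monotone, so the range-limited regression step does the imputing.

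**Size of the downward shift.** For a normal draw with mean μ and SD σ kept below 1, let a = (1 − μ)/σ and λ = φ(a)/Φ(a). The mean then moves by −σλ. Take an assumed residual SD of 0.191.
- Ensifentrine, μ = 0.736: a = 1.382, λ = 0.167, shift −0.032.
- Placebo, μ = 0.695: a = 1.597, λ = 0.118, shift −0.023.

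These are shifts at the average prediction. Averaged over patients with different baselines they are larger, because those predicted near 1 lose most.

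**Simulation.** It used 500 vs 300 patients, the SAP's three value sets, and imputation on treatment, region, strata and baseline, followed by ANCOVA. The comparison is with the same data before deletion. In the table the assumed baseline mean is 0.70 and missingness is unrelated to baseline.

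| Missing, ensifentrine/placebo | Full data | Unrestricted | Range-limited | Range-limited ÷ full |
|---|---|---|---|---|
| 15%/15% | 0.0401 | 0.0400 | 0.0383 | 0.954 |
| 20%/20% | 0.0401 | 0.0400 | 0.0377 | 0.939 |
| 13%/17% | 0.0397 | 0.0396 | 0.0398 | 1.001 |
| 12%/18% | 0.0401 | 0.0399 | 0.0410 | 1.023 |

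At 15%/15% the mean imputed values were:
- Ensifentrine: true 0.737, unrestricted 0.736, range-limited 0.683.
- Placebo: true 0.695, unrestricted 0.695, range-limited 0.654.

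With an assumed baseline mean of 0.82, the last column is 0.948 at 15%/15%, 0.929 at 20%/20% and 1.043 at 12%/18%.

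**Why the direction changes.** Let m be the missing rate and δ the mean loss per imputed value. The bias in the difference is about −(m_E δ_E − m_P δ_P), with E for ensifentrine and P for placebo. At 15%/15%, δ_E = 0.7362 − 0.6829 = 0.0533 and δ_P = 0.6953 − 0.6538 = 0.0415.
- 15%/15%: −0.15 × (0.0533 − 0.0415) = −0.0018. The simulated gap between range-limited and unrestricted is −0.0017.
- Break-even: m_P/m_E = 0.0533/0.0415 = 1.28, which agrees with the near-zero bias at 13%/17%.
- 20%/10%: −(0.0107 − 0.0042) = −0.0065, about 16% of 0.0401. Simulated ratios ran from about 0.79 to 0.94.
- 10%/20%: −(0.0053 − 0.0083) = +0.0030, about 7% of 0.0401. Simulated ratios ran from about 1.00 to 1.05.
- 10%/20% with no true effect, taking δ = 0.0415 in both arms: +0.10 × 0.0415 = +0.004.

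**Against the standard error.** At 15%/15%, 0.0018/0.0141 = 0.13 SE. At 20%/20%, 0.0025/0.0143 = 0.17 SE. At 20%/10%, 0.0065/0.0141 = 0.46 SE.

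**Missingness related to baseline.** With baseline 0.82 and 15% missing per arm, the full-data difference is 0.0285. Unrestricted imputation gives 0.0274 (96%) and range-limited 0.0262 (92%). About half of that shortfall is therefore not due to the limits.

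**VAS.** With assumed baseline mean 65, effect 3 and 15% missing per arm, the differences are 2.92 (full) and 2.88 (range-limited), a ratio of 0.99.

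**The case against.** The strongest reply is that the effect is small, rests on assumed distributions and touches an endpoint outside the hierarchy. All of that is true and fixes the severity. With equal missingness the shift is below 0.2 SE, and the trial requires symptomatic patients (mMRC of at least 2), so the share near the ceiling is uncertain.

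The method is also deliberate: the SAP cites a simulation study on limited-range variables. That source is not available here, so the citation neither supports nor refutes the choice for this index.

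SAP 16.3.4 plans an analysis without imputation, which truncation cannot affect. It is confined to on-treatment data, however, so it answers a different question from the treatment-policy approach and does not replace an unrestricted imputation.

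The SGRQ and E-RS precedent is not clean. SAP 16.2.2.3 gives the range method sensitivity status for them, but 16.2.3.1 sends all change-from-baseline variables to it. The case therefore rests on the arithmetic and not on precedent.

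A reader might also infer that one MIN= value cannot serve three value sets with floors of −0.590, −0.285 and −0.573. The SAP sets limits by endpoint without giving numbers and does not commit to one floor. Nothing in the calculations turns on the floor, so this is not a defect.

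**Conclusion.** The point holds for the health index, at low severity. Range-limited imputation lowers imputed index means by about 0.03 to 0.05. The treatment difference is then:
- about 3 to 7% too small with 15 to 20% missing in both arms;
- about 6 to 20% too small with 20% missing on ensifentrine and 10% on placebo;
- slightly too large with 10% and 20%, or about +0.004 for ensifentrine when there is no true effect.

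The shift is about 0.2 SE or less with equal missingness and up to about 0.5 SE otherwise. Index distributions, effect sizes and missing rates are all assumptions.

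Three stronger readings are tempting and not supported. The first is that the method always pulls the difference towards zero and is therefore conservative; this fails once placebo has about 4 percentage points more missing data. The second is that unrestricted imputation exactly recovers the full-data result. That holds only when missingness does not depend on baseline; otherwise it gave 94 to 99%. The third is that the whole EQ-5D-5L and TDI are affected alike. The VAS stays within about 2% of full data, and TDI limits lie far from the data.

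**What to change.** In SAP 16.2.2.3, 16.3.2 and 16.3.3, assign the EQ-5D-5L health index to the 16.2.2.1 imputation without MIN= and MAX= as the main analysis. Move the VAS with it so that both outcomes use one method. Keep the range-limited version as a sensitivity analysis, listed in 16.3.4 with its numerical limits stated. TDI needs no change on this account.

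The cost is two options removed from the SAS code for the main run, a few cross-references and one extra sensitivity table. No new data are needed. The downside is that some imputed values will exceed 1 or 100. That does no harm to an estimated mean, but the SAP should say that such values are expected and are not patient-level scores.

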16.2.2.4. Other methods

As a sensitivity analysis, other missing data method for key secondary endpoints will follow the average imputation and tipping point approach taken for primary endpoint outlined in section 16.1.2 of the SAP.

16.2.3. ANALYSIS OF SECONDARY EFFICACY VARIABLES

16.2.3.1. Change from baseline variables, incl. TDI

All variables used in change from baseline analysis (incl. average FEV₁ AUC_{0-4h}, peak FEV₁, morning trough FEV₁, evening trough FEV₁, mean weekly E-RS™: COPD, SGRQ, mean weekly rescue medication and TDI) will be analyzed using ANCOVA approach, as described in section 16.1.3 of the SAP. BDI will be used as a baseline for TDI. Missing data will be imputed using imputation described in section 16.2.2.3 of the SAP.

Model assumptions will be tested and solved, if failed, as per section 16.1.3 of the SAP.

A plot of the mean change from baseline FEV₁ to each post-dose FEV₁ result over time will be created by subgroups of actual background medication strata and actual smoking strata, visit and treatment group.

A plot of the least squares means change from baseline to event over time will be presented (based on the ANCOVA analysis). Events will include weekly mean total E-RS score, SGRQ and weekly mean rescue medication use.

Only FEV₁ measurements with BTR grades “Acceptable” and “Borderline Acceptable” are used in the analysis.

16.2.3.2. Proportion of SGRQ total responders

Proportion of responders, with an improvement from baseline in SGRQ total score of 4 or more will be analyzed using a logistic regression model with fixed effects for treatment, region, actual background medication strata and actual smoking strata at baseline and baseline SGRQ total score as covariate. Missing data will be imputed as described in section 16.2.2.3.

16.2.4. SENSITIVITY ANALYSIS OF SECONDARY EFFICACY VARIABLES

For the key secondary endpoints, the following sensitivity analysis will be performed at Week 12.

Subgroup analysis as specified in section 7.5 of the SAP.

- ANCOVA analysis with average imputation, as described in section 16.2.2 of the SAP.
- ANCOVA analysis with MI, only considering baseline and Week 12 (for lung function parameters) in the imputation model, as described in section 16.1.2 and 16.1.3 of the SAP.
- ANCOVA analysis with MI using the range data method as described in section 16.2.2.3 for SGRQ total score and weekly mean total E-RS.
- Tipping point approach, as described in section 16.1.2 of the SAP.
- Analysis with MI method, as described in sections 16.2.2 and 16.2.3 of the SAP, based on PP population.

For FEV₁ key secondary endpoints (FEV₁ AUC_{0-4h}, peak FEV₁, morning trough FEV₁) additional sensitivity analysis will be performed:

- MMRM model with treatment, visit and treatment by visit as fixed effect; baseline as covariate; patient as random factor; unstructured covariance by visit. If the model does not converge a compound symmetry covariance structure will be used. Kenward-Roger method will be used to estimate the model degrees of freedom. weeks.

For weekly mean E-RS total score and SGRQ total score, additional analysis will be performed:

- For weekly mean E-RS total score at 6, 12 and 24 weeks, using ANCOVA approach, as described in section 16.2.3 of the SAP, all patients with baseline weekly mean = 0 will be excluded.
- For SQRG total score at 6, 12 and 24 weeks, using ANCOVA approach, as described in section 16.2.3.1 of the SAP, all patients with baseline assessment done after dosing time and date will be excluded.

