9.0 STATISTICAL CONSIDERATIONS

9.1 Statistical Hypotheses

The aim of this study is to show superiority of ensifentrine over placebo regarding selected efficacy measures. The null hypothesis to be tested for each endpoint will be that there is no difference between ensifentrine and placebo, against the alternative hypothesis that ensifentrine is better than placebo. All tests will be two-sided at a 5% significance level. Primary and key secondary endpoints used for claims will be tested in a sequential order to preserve the alpha level. Testing will stop once a not significant result is achieved. Test order will be FEV₁ AUC_{0-12h} at 12 weeks, peak FEV₁ at 12 weeks, weekly mean E-RS total symptom score at week 24, SGRQ total score at Week 24, morning trough FEV₁ at Week 12, FEV₁ AUC_{0-4h} at 12 weeks and proportion of SGRQ responders at 24 weeks.

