
Secondary
	
To evaluate the effect of ensifentrine on COPD symptoms.
	
Patients with moderate to severe COPD aged 40-80 years (inclusive) that are in the mITT population. See full list of inclusion and exclusion criteria in sections 5.1, 5.2 and 5.3 of study protocol.
	
Change from baseline (i.e. mean over the last 7 days of run-in) to the mean weekly value at Week 24 in COPD symptoms, as measured by daily diary (Evaluating Respiratory Symptoms for COPD [E-RS™;COPD])
	
Regardless of whether the patient discontinues treatment prematurely and regardless of major protocol deviation, as per the Treatment Policy strategy.
	
Estimated treatment difference at the end of the double-blind period (and corresponding 95% CI) from ANCOVA analysis.

Secondary
	
To evaluate the effect of ensifentrine on health-related quality of life.
	
Patients with moderate to severe COPD aged 40-80 years (inclusive) that are in the mITT population. See full list of inclusion and exclusion criteria in sections 5.1, 5.2 and 5.3 of study protocol.
	
1. Change from baseline in the St. George's Respiratory Questionnaire (SGRQ) total score at Week 24 2. Proportion of SGRQ responders at Week 24
	
Regardless of whether the patient discontinues treatment prematurely and regardless of major protocol deviation, as per the Treatment Policy strategy.
	
1. Estimated treatment difference at the end of the double-blind period (and corresponding 95% CI) from ANCOVA analysis. 2. Odds ratio for proportion of responders with an improvement of at least 4 units at the end of the double-blind period (and corresponding 95% CI) from logistic

[figure not shown]
						regression analysis.
--	--	--	--	--	--	----------------------

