7.2. MULTICENTER STUDIES

This study will be conducted by multiple investigators at multiple centers internationally. Randomization to treatment arms is not stratified by country/ center.

When specified, statistical analysis will be adjusted for geographic region. Geographic region will be categorized as shown in Table 3:.

Table 3: Geographic Regions

Geographic Region	Country
Europe	Belgium, Bulgaria, Denmark, Hungary, Poland, Slovakia, Estonia, Spain
North America	United States, Canada

7.3.MISSING DATA

Missing safety data will not be imputed.

All data collected during the scheduled visits for patients on-treatment and off-treatment, for patients with treatment withdrawal, as well as the end-of-study visits for patients withdrawing from the study will be used for analysis performed on the mITT and that the remaining missing values will be handled as described in sections 16.1.2, 16.2.2 and 16.3.2 of the SAP.

7.4.MULTIPLE COMPARISONS/ MULTIPLICITY

To address multiplicity in the analysis of the endpoints, statistical testing of the primary endpoint and key secondary endpoints will be done in the hierarchical order (listed below). Initially the primary endpoint will be checked to see if comparison between active treatment and placebo is statistically significant. If yes, the first key secondary endpoint will be evaluated. If yes, the next key secondary endpoint will be evaluated. This process will continue until either all endpoints are evaluated, or if one of the endpoints' comparison is not significant.

Order of the endpoints that will be used for the hierarchical testing:

1. Change from baseline FEV₁ to FEV₁ AUC_{0-12h} at Week 12
2. Change from baseline FEV₁ to peak FEV₁ at Week 12
3. Change from baseline (i.e. mean over the last 7 days of run-in) to the mean weekly value at Week 24 in COPD symptoms, as measured by daily diary (E-RSTM:COPD)
4. Change from baseline in the SGRQ total score at Week 24
5. Change from baseline FEV₁ to morning trough FEV₁ at Week 12
6. Change from baseline FEV₁ to average FEV₁ AUC_{0-4h} at Week 12
7. Proportion of SGRQ responders at Week 24

7.5.EXAMINATION OF SUBGROUPS

Subgroup analyses will be conducted as stated in the efficacy analysis and disposition sections. Primary aim for the subgroup analysis is to check whether there are differences in treatment effect between strata or subgroups, which will be tested through interaction. For each analysis

by subgroup the results will be summarized as follows:

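### SAP 16.2.4 sets the key-secondary sensitivity analyses at Week 12, but E-RS total, SGRQ total and SGRQ responders are tested at Week 24, and the SAP's other sections do not settle the conflict

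*SAP*

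**What the plan says.** SAP 16.2.4 begins: "For the key secondary endpoints, the following sensitivity analysis will be performed at Week 12". Six items follow: subgroup analyses; "ANCOVA analysis with average imputation, as described in section 16.2.2 of the SAP"; a multiple imputation (MI) using only baseline and Week 12, marked as applying to lung function; "ANCOVA analysis with MI using the range data method as described in section 16.2.2.3 for SGRQ total score and weekly mean total E-RS"; the tipping point; and an analysis in the per-protocol (PP) population.

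After that list come an MMRM for the three FEV1 key secondaries and two further analyses at Weeks 6, 12 and 24. One drops patients whose baseline E-RS mean is zero. In the other, for SGRQ, "all patients with baseline assessment done after dosing time and date will be excluded".

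The tested visits are stated consistently elsewhere. Protocol 9.1 puts in the test order "weekly mean E-RS total symptom score at week 24, SGRQ total score at Week 24". SAP 7.4 lists "Change from baseline in the SGRQ total score at Week 24", and the SAP estimand table lists "Proportion of SGRQ responders at Week 24".

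Several places promise sensitivity analyses without naming a visit:
- SAP 16.2.2.4 says that "other missing data method for key secondary endpoints will follow the average imputation and tipping point approach taken for primary endpoint".
- SAP 16.2.2.3 describes range-restricted MI as the sensitivity method for SGRQ total and E-RS.
- SAP Table 2 marks the PP population for secondary endpoints.
- Protocol 9.4.1 promises a PP evaluation of the key secondaries, and protocol 9.4.4 a worst-case imputation.

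**The concern.** The main analyses of E-RS and SGRQ at Week 24 assume that data are missing at random. The tipping point and the opposite-arm average imputation test that assumption, and the PP analysis tests dependence on protocol adherence. All three are informative only at the visit that carries the claim. Withdrawals accumulate, so no fewer patients will have left by Week 24 than by Week 12. A Week 12 result could therefore look reassuring while leaving the Week 24 conclusion unexamined.

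The lead-in cannot be read as meant for lung function alone. The range-MI bullet beneath it names only SGRQ total and E-RS, and neither is tested at Week 12.

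**Working it through.** The plan attaches no figure to this point, so the check sets the passages side by side.

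**Step 1: tested visit against sensitivity visit.** Position 1 in SAP 7.4 is the primary endpoint; positions 2 to 7 are the key secondaries.

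| Position and endpoint | Tested visit (SAP 7.4) | Visit set in SAP 16.2.4 | Match |
|---|---|---|---|
| 2. Peak FEV1 | Week 12 | Week 12 | yes |
| 3. E-RS total | Week 24 | Week 12 | no |
| 4. SGRQ total | Week 24 | Week 12 | no |
| 5. Morning trough FEV1 | Week 12 | Week 12 | yes |
| 6. FEV1 AUC0-4h | Week 12 | Week 12 | yes |
| 7. SGRQ responders | Week 24 | Week 12 | no |

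Mismatches: 3 of 6. Protocol 9.4.1 and SAP 16.2.2.1 name only five continuous endpoints when they list key secondaries. On that narrower reading it is 2 of 5. The gap is 24 − 12 = 12 weeks.

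**Step 2: which checks matter.** Of the six items under the lead-in, subgroups are neither a missing-data nor a PP check, and the lung-function MI belongs at Week 12. Four remain: average imputation, range MI, tipping point and PP. For the two continuous endpoints that is 2 × 4 = 8 endpoint-check pairs. Responders add at most 3, since range MI is not listed for them. SAP 16.2.4 places none of these at Week 24.

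**Step 3: do the Week 24 items in 16.2.4 fill the gap?** No. Both remove patients for baseline reasons and leave the treatment of missing outcomes unchanged.

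**Step 4: do the visit-free passages settle it?** They show intent, but they do not assign a visit. SAP 16.2.4 is the only section that does, and it says Week 12. SAP 3.3 does not list a restriction to Week 12 as a change from the protocol.

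**Step 5: related inconsistencies.**
- *Imputation references.* SAP 16.2.2.1 makes unrestricted MI the method for the key secondary analyses, and 16.2.2.3 makes range MI the sensitivity method for SGRQ total and E-RS. Yet 16.2.3.1 sends the main analyses to 16.2.2.3. Read literally, main and sensitivity imputation coincide. SAP 16.2.3.2 also sends responders to 16.2.2.3, while the steps for re-deriving response and pooling odds ratios are in 16.2.2.2.
- *Responders.* The tipping point in SAP 16.1.2 and the average-imputation bullet are worded for ANCOVA; responders are analysed by logistic regression. SAP 3.3 openly drops the protocol's non-responder analysis, so no responder-specific missing-data check is written out.
- *MMRM.* Protocol 9.4.1 covers 5 continuous key secondaries and SAP 16.2.4 covers 3. SAP 3.3 does not mention the removal of SGRQ total and E-RS.
- *PP set.* Protocol 9.3 removes important deviations that affect efficacy assessments in general. SAP 5.7 narrows this to Week 12 lung function. SAP 3.3 lists only the Day 74 rule.

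**The case against.** The strongest reply is that SAP 16.2.4 should not be read alone. SAP 16.2.2.3, 16.2.2.4 and Table 2, with protocol 9.4.1 and 9.4.4, all commit to these checks for the key secondaries, and SAP 7.4 defines those endpoints with their visits. The average imputation in SAP 16.1.2 uses the mean change at the particular visit. The Week 12 wording is then probably a drafting slip, and the output shells, which are not in the documents, may already state the right visit. This stands to the extent that it limits the claim. A reader might infer that the plan has no missing-data or PP check at Week 24; the documents do not support that. They support a conflict in which the one passage naming a visit names the wrong one for these endpoints.

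A reader might also infer that the PP set breaches the protocol because a patient who stops treatment after Day 74 stays in it. It does not: protocol 9.3 has no discontinuation-day rule, and the SAP's Day 74 exclusion is stricter on that point and is declared. The estimand is treatment policy, so off-drug data belong in the main analysis. Only the unlisted narrowing to Week 12 lung function is a discrepancy.

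The loss of the responder non-responder analysis is likewise a declared decision with a stated reason, and is not a result of the Week 12 wording. The MMRM also assumes missing at random, so its absence removes little stress-testing; that point concerns an undeclared change. For subgroups, the protocol promises only selected secondary endpoints, so no commitment is broken.

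**Conclusion.** The conflict is real and should be corrected before database lock. SAP 16.2.4, followed literally, puts the robustness checks for 3 of 6 key secondaries (2 of 5 if only the continuous ones count) at a visit where those endpoints are not tested. Nothing in the SAP expressly assigns them to Week 24.

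The main MI analyses at Week 24, the primary analysis and the hierarchy are untouched. The imputation cross-references and the two omissions from SAP 3.3 (MMRM scope and PP narrowing) are genuine but secondary, and changing the visit does not resolve them.

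This rests on two things: that the lead-in governs the whole list beneath it, which the range-MI bullet supports, and that the unseen output shells do not already correct the visit.

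**What to change.** 1. In SAP 16.2.4, replace the Week 12 lead-in with *at the visit tested in Section 7.4 (Week 12 for the FEV1 endpoints; Week 24 for E-RS total, SGRQ total and SGRQ responders)*. Leave the lung-function MI bullet at Week 12.
2. Run the MMRM for SGRQ total and E-RS as protocol 9.4.1 states, or list its removal in SAP 3.3.
3. Align 16.2.3.1 and 16.2.3.2 with 16.2.2.1 and 16.2.2.2, so that range MI differs from the main imputation. For responders, write out the tipping point: shift the imputed SGRQ scores by k, re-derive response (improvement of 4 or more) in each imputed dataset, refit the logistic model and pool as in 16.2.2.2.
4. List the narrowing of PP deviations to Week 12 lung function in SAP 3.3, or restore the protocol wording for the Week 24 endpoints. A separate Week 24 discontinuation cut-off is optional; the documents neither require one nor supply a day for it.

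The cost is SAP text and a few extra tables. No new data are needed.
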